9. STATISTICAL ANALYSIS

The statistical analysis will be described in the statistical analysis plan (SAP), written by the biostatistician, which is binding and will be finalized before database lock or before any other analysis takes place.

9.1 Baseline characteristics:

Both an intention to treat (ITT) and a per-protocol (PP) approach will be used to define the analysis populations in both phase 2 and phase 3 studies. In the Intention-to-Treat analysis, all participants will be analyzed according to their randomized allocation, even in case they do not receive the randomized treatment, show protocol violations prior to or during the study.

In the per-protocol analysis only participants who received PEP as planned, have completed follow-up, and follow the protocol as planned are included.

In the phase 2 study, the PP population will be the primary analysis population as indicated for non-inferiority studies by the ICH-E9 guidelines. For the phase 3 study, the intention to treat will be the primary approach.

The number of participants screened and enrolled or excluded will be summarized according to reason for exclusion. Of the enrollees, the number of patients discontinued or lost to follow-up will be recorded by reason and time of discontinuation. These figures will be summarized in a CONSORT flow diagram.

Subjects in each treatment group will be described according to baseline characteristics. The description will be in terms of medians and interquartile ranges for continuous variables and using counts and percentages for categorical variables. Standard statistical tests of significance of imbalance in baseline characteristics will be performed.

9.2. Phase 2 study:

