The total enrolment to date in the PEOPLE trial in Comoros has been approximately 86,000. Out of 15,569 persons eligible for PEP in 2019, 12,101 (83.1%) actually took PEP. A preliminary analysis based on data for the second year (2020) shows an incidence of approximately 1.1 per 1,000 (96 new cases). In a Poisson model controlled for differences in baseline prevalence and with village nested in island as random effects to control for contextual confounding, we found incidence rate ratios of 1.23, 0.78 and 0.89 when comparing respectively arms 2, 3 and 4 to arm 1, the comparator arm. None of these associations was statistically significant ($p \geq 0.70$). At individual level the effect of PEP controlled for distance to nearest index case was a borderline statistically significant reduction in risk of leprosy, with an incidence rate ratio of 0.48 (95% confidence interval 0.21-1.13).

Based on the individual effect of SDDR-PEP and taking into account the fact that less than two out of three years of follow-up have passed, the associations at study arm level might still become more pronounced but we do already want to test a stronger PEP regimen making use of the established set up. The regimen we intend to test is a combination of rifampicin and bedaquiline, hereafter referred to as 'Bedaquiline enhanced post exposure prophylaxis' or BE-PEP. Rifampicin will be provided at a dose of 10 mg/kg, the WHO standard, i.e. 600 mg for an adult. Bedaquiline will be provided at a dose of 800 mg for an adult, double the daily dose used in treatment of rifampicin resistant tuberculosis.[6] Based on pharmacological considerations and pre-clinical studies we expect this regimen to have a synergistic action against *M. leprae*. BE-PEP will be administered as a single dose, repeated after four

weeks only for household contacts, as preliminary data from the PEOPLE trial show that their residual risk is still up to three times higher when compared to the rest of the population.

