4.5.4 Lost to follow-up

Patients will be considered lost to follow-up if not present during the fourth and final survey round, after one additional attempt has been made to contact them. In this case follow-up time will be calculated based on the last available follow-up.

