- 6 In arm 1, household contacts of an index case will receive an extra dose of BE-PEP after 4 weeks
- 7 Household members living in a household eligible based on the PEP zone but absent during screening can be enrolled and screened during the 1st dose PEP administration visit and receive PEP if eligible
- 8 If leprosy or TB clinical signs present, after collecting a specific ICF for leprosy index case or TB suspicion, samples to be collected.
- 9 +-25 after the last person screening (=V1) in a village during the annual screening round
- 10 +-30 days after the last person screening (=V1) in a village during the annual screening round

For all visits, especially important for safety FU visits: if a participant is not home (and is not permanently absent), the site staff should visit the household at least one more time to conduct the visit. Participants will be informed they may always report adverse events by phone

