9.3. Phase3 study

9.3.1. Primary analysis

The main analysis will be to assess the effect of BE-PEP at individual level. Because in the first study year anyone living within 100 meter of an index case over the period 2018-2023 will be eligible for PEP and if this is more than 50% of the village population the entire village population above 2 years of age will be eligible where for the first year any leprosy case included in the study population detected

during the annual village screening or in the preceding five-year period, i.e. since January 1st, 2018 will be considered an index case. The following years, any leprosy case detected after the last year's screening up to and including the village's screening round of the current year will be considered an index case. Therefore, we assume that in the first year there will be blanket coverage with either SDR-PEP or BE-PEP. We will fit a Poisson model adjusted for follow-up time as an offset term with village nested in island as random effect and type of PEP (BE-PEP or SDR-PEP), as explanatory variable. Those who did not receive PEP and those below the age or weight limits for BE-PEP will be excluded from this analysis, SDR-PEP will be our reference category. Outcome variable will be incident leprosy. We will consider all cases diagnosed after the first intervention round in 2023, until the final survey in 2026.

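### Read literally, the phase 3 per-protocol set drops PEP recipients with partial follow-up that the Poisson offset can use; a strict reading of PEP as planned could also remove higher-risk contacts from arm 1 only

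*Protocol*

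**What the plan says.** Protocol section 9.1 states that an intention-to-treat and a per-protocol approach "will be used to define the analysis populations in both phase 2 and phase 3 studies". The per-protocol rule is given once: "In the per-protocol analysis only participants who received PEP as planned, have completed follow-up, and follow the protocol as planned are included". On status it says: "For the phase 3 study, the intention to treat will be the primary approach".

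Three other places bear on how the rule works in phase 3.

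- **Follow-up.** Section 4.5.4: "Patients will be considered lost to follow-up if not present during the fourth and final survey round", after one further contact attempt. It goes on: "In this case follow-up time will be calculated based on the last available follow-up".
- **Model.** Section 9.3.1: "We will fit a Poisson model adjusted for follow-up time as an offset term". It excludes people who did not receive PEP and those below the BE-PEP age or weight limits.
- **Repeat administration.** Table 3, note 6 (section 5.1): "In arm 1, household contacts of an index case will receive an extra dose of BE-PEP after 4 weeks". The Synopsis gives the reason, which is that for household contacts "their residual risk is still up to three times higher when compared to the rest of the population".

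The SAP supplied covers phase 2 only. Its deviation table (SAP section 5.1.2, Table 1) makes the same rule concrete for a single administration and 30 days of follow-up. Nothing supplied does so for phase 3.

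**The concern.** The rule suits phase 2. Carried into a four-round cluster trial, it raises two issues.

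**Completion.** If completed follow-up means not being lost in the sense of 4.5.4, a person dosed in 2023, examined and free of leprosy at the next two rounds, and absent at the fourth contributes nothing. Section 4.5.4 would count that person's time to the last follow-up, and the offset in 9.3.1 exists for unequal follow-up. The per-protocol set would condition on an event that comes after the exposure time being analysed, and would lose person-time in both arms with no gain.

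**Administration.** Only arm 1 household contacts can be due a repeat. If PEP as planned is read to exclude those who were due one and missed it, people can leave arm 1 for this reason while comparable arm 2 contacts stay. Because household contacts carry more risk, that lowers the arm 1 rate even if the two regimens are equally effective.

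At stake is how useful the per-protocol result is as a check on the main phase 3 estimate. The trial is unblinded, so settling the definition late would also leave room for choice after results are visible.

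**Working it through.** **1. Reproduce the design figure.** Inputs from Protocol section 4.3: p0 = 0.0033 and p1 = 0.00165 over three years, k = 0.4, n = 1,708 per cluster (2,819 × 0.73 × 0.83 = 1,708), alpha 0.05 (taken as two-sided), power 90%. The cluster formula with the pair-matched constant is

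c = 2 + (1.960 + 1.282)² × V, where V = [p0(1−p0)/n + p1(1−p1)/n + k²(p0² + p1²)] / (p0 − p1)².

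- Binomial part: 2.890 × 10⁻⁶. Between-cluster part: 0.16 × (0.0033² + 0.00165²) = 2.178 × 10⁻⁶. Denominator: 0.00165² = 2.7225 × 10⁻⁶.
- V = 1.862, so c = 2 + 10.507 × 1.862 = 21.56, which rounds up to 22 as stated. Also 22 × 2 × 1,708 = 75,152, as stated.
- Power at 22 = Φ(√(20/V) − 1.960) = Φ(3.278 − 1.960) = 90.6%.

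The calculation allows for uptake of PEP (83%) but has no allowance for loss to follow-up.

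**2. Apply the completion rule.** Let r be the share of recipients present at the final survey and replace n by 1,708 × r. The documents give no phase 3 value for r. The 72.3% row is 62,266 screened out of 86,160 under follow-up in one PEOPLE round in Comoros (section 1.1), used only as a proxy.

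| r | n per cluster | V | Power at 22 per arm |
|---|---|---|---|
| 100% | 1,708 | 1.862 | 90.6% |
| 95% | 1,623 | 1.917 | 89.8% |
| 90% | 1,537 | 1.980 | 88.9% |
| 72.3% | 1,234 | 2.269 | 84.4% |

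Person-time lost, if those absent at the end had 1 to 2 of 3 years observed (assumed): share = d·y / [d·y + 3(1−d)], with d = 1 − r. At d = 10% this is 3.6% (y = 1) to 6.9% (y = 2). At d = 27.7% it is 11.3% to 20.4%.

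**3. Apply a strict repeat rule in arm 1.** Let h be the household-contact share of recipients, m the share of contacts who were due a repeat and missed it, and R their risk relative to other recipients. With no true effect and no adjustment, the per-protocol rate ratio is

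{[(1−h) + h(1−m)R] / (1 − hm)} / [(1−h) + hR].

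R = 3 is the Synopsis upper figure. Neither h nor m is in the documents, so both are assumed.

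- h = 0.03, m = 0.10: 1.0542 / 1.06 = 0.994
- h = 0.05, m = 0.20: 1.0808 / 1.10 = 0.983
- h = 0.10, m = 0.30: 1.1443 / 1.20 = 0.954

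**4. Scale.** Under the null, each arm expects 0.0033 × 22 × 1,708 = 124 cases. Ignoring clustering, the standard error of the log rate ratio is √(2/124) = 0.127, and the 95% limits are a factor of about exp(1.96 × 0.127) = 1.28 either way. A shift of 1 to 5% is small beside that.

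**The case against.** The strongest case against is that the documents do not state the harsh reading, that the analysis is not primary, and that details are left to a SAP. Much of this stands.

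- **A reader might infer that section 9.1 requires two administrations for every arm 1 household contact.** It does not. The remarks on PEP distribution in section 4.2 plan one administration that year for contacts absent at the first distribution and reached at the second. Table 3 rechecks eligibility before the repeat, so a contact not re-dosed because of that check has arguably followed the plan. Only contacts who were due a repeat and missed it are in question. The SAP's phase 2 table, which treats under-dosing as a minor deviation, also shows that less drug need not mean exclusion, though it does not govern phase 3.
- **A reader might infer that a case diagnosed early who later leaves is dropped.** That is possible but not stated. Section 9.1 does not say whether diagnosis counts as completing follow-up.
- **The one-arm shift assumes no adjustment.** The Synopsis and section 3.1 plan control for distance to the nearest index case, which would absorb much of the change in case mix, though not selection among household contacts. The model sentence in 9.3.1 omits distance, so the plan should confirm it.
- **A larger shift might be computed from the 7-8-fold gradient in Annex 1.** That gradient compares household members with people living 100 metres or more from a case. Other PEP recipients mostly live closer, so it has the wrong reference group and is not used here.
- **Low consequence.** Intention to treat is primary, and section 9.3 specifies no separate per-protocol model.

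What the objection does not answer is the conflict between the completion condition in 9.1 and the handling of partial follow-up in 4.5.4 and 9.3.1.

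**Conclusion.** The point holds in two parts of unequal strength.

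**Completion (firm).** The stated rule, read with the only phase 3 definition available, removes usable person-time and conditions on later presence. The cost is mainly precision: about 91% power falls to about 89% at 90% presence and about 84% at 72%. The figures assume that the section 4.3 inputs hold and that dropping people acts as a proportional cut in cluster size. The 72% is a one-round proxy from another trial and may not describe PEP recipients at the final phase 3 survey. The rule acts on both arms, so no direction of bias is claimed for it.

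**Missed repeat (conditional).** If the strict reading is adopted, the exclusion can occur in arm 1 only and favours BE-PEP: a null rate ratio of about 0.95 to 0.99 at R = 3 without adjustment, and closer to 1 with the planned distance adjustment. The household share (3-10%) and missed-repeat share (10-30%) are assumptions.

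A reader might conclude that agreement between the per-protocol and main analyses would be false reassurance. The documents do not support that: a shift of 5% or less is small against a target rate ratio of 0.50 and the random error in step 4 of the working. The phase 3 primary analysis is not affected.

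**What to change.** Give phase 3 its own per-protocol definition in Protocol section 9.1 and in the phase 3 SAP, before any phase 3 analysis:

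1. Delete the completed-follow-up condition for phase 3. Count person-time to diagnosis or last examination, in line with section 4.5.4, and keep cases diagnosed before loss.
2. State that a missed repeat does not by itself remove an arm 1 household contact from the set. If a full-course set is wanted, either leave household contacts out of both arms or adjust for household-contact status.
3. Confirm that the per-protocol model carries the distance adjustment described in the Synopsis and section 3.1, which the model sentence in 9.3.1 does not list.

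The cost is about one paragraph in the protocol and the matching SAP text, with no new data. The downside is that the per-protocol set will lie closer to the recipients-only set already used in 9.3.1 and so adds less as a separate analysis. Item 1 is worth making regardless; item 2 leaves a choice to the sponsor.

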9.2.1. Primary analysis

The main objective about the difference in QTc between the two arms 24 hours after treatment administration will be assessed using a two-sample t-test.

9.2.2. Secondary analysis

Baseline frequency of ALT/AST elevations and QTc prolongations in the population, before and after study drug administration will be estimated using 95% confidence intervals for each time point and by study arm. No formal comparison will be done between time points or between arms.

Potentially frequent adverse events such as gastro-intestinal (nausea, vomiting), nervous system-related (headache, dizziness) and cutaneous reactions will be tabulated and presented using standard descriptive statistics. A comparison between the two arms will be done using Fisher's exact test.

9.3. Phase3 study

9.3.1. Primary analysis

The main analysis will be to assess the effect of BE-PEP at individual level. Because in the first study year anyone living within 100 meter of an index case over the period 2018-2023 will be eligible for PEP and if this is more than 50% of the village population the entire village population above 2 years of age will be eligible where for the first year any leprosy case included in the study population detected

during the annual village screening or in the preceding five-year period, i.e. since January 1st, 2018 will be considered an index case. The following years, any leprosy case detected after the last year's screening up to and including the village's screening round of the current year will be considered an index case. Therefore, we assume that in the first year there will be blanket coverage with either SDR-PEP or BE-PEP. We will fit a Poisson model adjusted for follow-up time as an offset term with village nested in island as random effect and type of PEP (BE-PEP or SDR-PEP), as explanatory variable. Those who did not receive PEP and those below the age or weight limits for BE-PEP will be excluded from this analysis, SDR-PEP will be our reference category. Outcome variable will be incident leprosy. We will consider all cases diagnosed after the first intervention round in 2023, until the final survey in 2026.

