respective village has been completed. For the first PEP distribution round in 2023, any leprosy case recorded during the first village screening that year or in the preceding five-year period, i.e. since January 1st, 2018, will be considered an index case. As of the 2nd annual screening round, any leprosy case detected after the screening of the previous year and up to and including the village's screening round of the current year will be considered an 'index case'. First eligibility at household level will be determined based on the distance of the household to the closest index case (Eligibility based on PEP zone). In both arms we will target anyone living within 100 meters of an index case or the entire village if more than 50% of the population are eligible. Afterwards the eligible households will be visited and individual inclusion and exclusion criteria for the annual PEP distribution will be checked before offering PEP to a study participant. Provision of PEP will start in 2023 and follow-up will continue for 4 years. Our main study outcome will be the comparison of leprosy risk in individuals that received standard WHO SDR-PEP versus individuals that received BE-PEP. In addition, we will compare the overall leprosy incidence over the follow-up period between the two study arms.

As stated above, our primary outcome measure will be the incidence rate ratio of leprosy between those who received BE-PEP and those who received the standard SDR-PEP. From this analysis we will exclude those not eligible for BE-PEP, i.e. children below 5 years of age and/or with a weight below 20 kg. We will fit a Poisson model with village nested in island as random effect and controlled for distance to the nearest index case at baseline. In addition, we will compute compare the incidence rate ratios between the entire BE-PEP and SDR-PEP arms over a period of 4 years starting at the first screening round up to the last follow up after 4 years, also based on a Poisson model with village nested in island as random effect. From this analysis we will not exclude anyone not eligible for BE-PEP.

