1.2 Rationale

As was explained above, based on preliminary data for the first year of follow-up of the PEOPLE trial and taken into account differences in baseline prevalence, in Comoros we find incidence rate ratios of 1.23, 0.78 and 0.89 when comparing respectively arms 2, 3 and 4 to arm 1, the comparator arm. None of these associations was anywhere near statistically significant ($p \geq 0.70$) and already we observe that during the second year of follow-up differences between intervention arms and comparator arm are not increasing. Though we do start seeing an effect at individual level, a marginally significant reduction in risk of 52%, we hypothesize that a more effective PEP regimen is required to not just prevent individual progression from asymptomatic infection to disease but to have an impact on transmission as well.

The setup of the ongoing PEOPLE trial provides an ideal context to test an alternative PEP regimen. A strong data collection system has been developed and extensively field tested, survey teams have been trained and quality assurance mechanisms established. Important lessons have been learnt to which our system has been adapted. Whereas in Madagascar we found a relatively low incidence to date, approximately 4.2 per 10,000 in the first year of follow-up, in Comoros the overall incidence over the first year of follow-up was still 11.1 per 10,000 per year, despite SDDR-PEP being provided in three of the four study arms. Moreover, there are some larger villages in Comoros that were not included in the PEOPLE trial out of concerns for an imbalance between study arms upon randomization, in these villages we continue to see high leprosy incidence, in the order of 20-30 per 10,000 per year over the past five years.

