Year 2	Phase 3 study	Screening Arm 1 & 2 + PEP intervention	Sampling leprosy patients	Sampling TB patients	
Year 3	Phase 3 study	Screening Arm 1 & 2 + PEP intervention	Sampling leprosy patients	Sampling TB patients	
Year 4	Phase 3 study	Final screening Arm 1 & 2	Sampling leprosy patients		PGL-I survey

Table 1: Time table BE-PEOPLE

Participants in the new villages will be asked for informed consent for baseline screening in 2022. Informed consent for the phase 3 intervention trial will be asked during the first intervention round in 2023, when we know to which study-arm villages have been randomized. Informed consent for the leprosy patient cohort will remain separate, the same applies to the TB patients being enrolled. For the PGL-I survey in 2026, separate informed consent will be asked ahead of the survey.

Figure 1 below shows how villages belonging to the various arms of PEOPLE will merge into BE-PEOPLE. We have dropped some villages that had a low incidence so far during the PEOPLE trial or a small population size. To arrive at the required sample size we will also include nine new villages, eight on Anjouan and one on Mohéli, the latter to be split into two clusters. Villages will be arranged by PEOPLE study arm and by island in order of decreasing prevalence during the 2022 baseline survey and regrouped into pairs. Within each pair they will be randomized to arm 1 or arm 2 of BE-PEOPLE.

[figure not shown]

Figure 1: Inclusion and randomization BE-PEOPLE (Phase 3) trial

The main outcome measure of BE-PEOPLE will be the incidence rate ratio of leprosy between individuals in arm 1 who received BE-PEP and individuals in arm 2 who received SDR-PEP, controlled for potential confounding by distance to nearest index case at baseline, as well as for contextual confounding through the use of a random effects model (village nested within island). To avoid a potential selection bias, those who received SDR-PEP but would not have been eligible for BE-PEP, i.e. children below the age of 5 or with a weight below 20 kg, will be excluded from this analysis. Details are described in chapter 9, 'Data analysis'.

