4.4 Randomization

For the phase 2 safety study we will first complete the final survey round of the PEOPLE study and then enumerate all those aged 5 years or above, weighing 20 kg or above and not currently suffering from leprosy. They will be divided into three age categories, 5-12 years, 13-17 years, and 18 years and above. We will then determine the overall proportions of the three age groups, the proportion multiplied by 150 will be the number of participants to be recruited per study arm for each age group. Next we will prepare sealed envelopes containing a note indicating either BE-PEP or SDR-PEP as PEP regimen, 300 in total. They will be divided into three groups with equal numbers per PEP regimen, one group of envelopes for each of the three age categories.

The next step will be to enroll the required numbers of adults (age 18 years and above) by visiting the households one by one and inviting eligible subjects to be enrolled. Each time a person agrees, an envelope will be drawn and either SDR-PEP or BE-PEP will be provided as indicated on the note inside the envelope. This process will continue until all envelopes for adults have been allocated. Provided no concerning adverse events are observed, the procedure will be repeated for the 13-17 years old. Again if no concerning adverse events are observed, the 5-12 years old will be enrolled following the same procedure. The remainder of the village population aged 2 years and above and not meeting other exclusion criteria will then be offered SDR-PEP.

Randomization for study arms 1 and 2 of the phase 3 study, will take place upon completion of the baseline survey. We will then arrange all villages by island and by group (former arm 1, 2, 3 or 4 or new villages), in order of decreasing prevalence. As was explained earlier, Fomboni, the capital of Mohéli, will be split into two clusters. Thus we will arrive at 22 pairs of clusters. Blocked randomization will be used to allocate clusters into the two study arms. The randomization schedules will be prepared by an independent sponsor biostatistician. The randomization list will be prepared using SAS 9.4 (SAS Institute, Cary NC).

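### The phase 3 primary model ignores the 22 pairs used for randomization, names the village rather than the cluster as its unit, and disagrees with the synopsis and section 3.1 on the distance covariate; if the pairing predicts incidence, its intervals are too wide.

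*Protocol*

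**What the plan says.** Protocol section 4.4 arranges the villages "by island and by group (former arm 1, 2, 3 or 4 or new villages), in order of decreasing prevalence" and concludes: "Thus we will arrive at 22 pairs of clusters". Section 3.1 specifies that the prevalence is that of the 2022 baseline survey and adds: "Within each pair they will be randomized to arm 1 or arm 2 of BE-PEOPLE". There are 43 villages but 44 clusters. Of the nine new villages, eight are on Anjouan and one (Fomboni) is on Mohéli, "the latter to be split into two clusters".

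For the primary analysis, section 9.3.1 says: "We will fit a Poisson model adjusted for follow-up time as an offset term with village nested in island as random effect". The only explanatory variable it names is type of PEP. Section 9.3.2 uses a similar model at village level, and the interim analysis in 9.3.3 refers back to both.

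The primary analysis is described differently elsewhere. The synopsis has it "controlled for distance to the nearest index case at baseline". Section 3.1 has it "controlled for potential confounding by distance to nearest index case at baseline" and points to chapter 9 for details, where distance does not appear. The SAP supplied covers phase 2 only (SAP section 1).

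**The concern.** Randomizing within pairs balances the arms on whatever the pairing factors predict. A model that leaves those factors out still treats the balanced variation between clusters as random noise when it computes the standard error. The standard error then exceeds the true sampling variation. A positive result remains valid, but a real effect smaller than the design effect is missed more often.

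Only one design factor, island, appears in the model, and it enters as a random level with two values. The preceding trial's arm comparison was adjusted for baseline prevalence (synopsis, sections 1.1 and 1.2). The new trial pairs on prevalence and then drops it.

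Two further points arise in the same sentence of 9.3.1:

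- **Unit.** Fomboni's two clusters are the only new clusters on Mohéli, so the stated sorting makes them one pair in opposite arms. Read literally, the model gives them one shared intercept.
- **Distance.** Two primary models are on record, one with distance and one without, in an unblinded trial. That leaves a choice open after data are seen.

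**Working it through.** **The plan's own figure.** Section 4.3 gives 3-year risks p0 = 0.0033 and p1 = 0.00165, cluster size m = 1,708 (2,819 × 0.73 × 0.83), CV k = 0.4, 90% power and α = 0.05 (taken as two-sided). The Hayes-Bennett formula is

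c = a + (1.960 + 1.282)² × [p0(1−p0)/m + p1(1−p1)/m + k²(p0² + p1²)] / (p0 − p1)²

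= a + 10.507 × (2.890×10⁻⁶ + 2.178×10⁻⁶) / 2.7225×10⁻⁶ = a + 19.56.

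The matched version (a = 2) gives 21.56, hence the stated 22 per arm, and 44 × 1,708 = 75,152 as stated. The unmatched version (a = 1) gives 20.56, hence 21. The sizing therefore fits a paired analysis, although the protocol does not say whether 0.4 is the CV before or after pairing.

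**How far could pairing predict incidence?** The documents give no direct figure. Section 1.2 says of larger villages left out of PEOPLE that "we continue to see high leprosy incidence, in the order of 20-30 per 10,000 per year", against 11.1 per 10,000 in the PEOPLE villages of Comoros. Section 4.3 calls the nine new villages large. That these are the same villages is an inference.

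- Against about 11 per 10,000: 20/11 = 1.82, 25/11 = 2.27, 30/11 = 2.73.
- The 34 retained villages exclude some dropped for low incidence. If all 96 cases fell in their 73,000 people, the rate is 96/73,000 = 13.2 per 10,000, an extreme bound. The ratios become 20/13.2 = 1.52 and 30/13.2 = 2.27.

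The working range is thus about 1.5 to 2.3, with 1 kept as the case of no contrast.

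**What each ratio implies.** Take 34 PEOPLE and 10 new clusters, with CV 0.34 (the PEOPLE figure, section 4.3) within each group. At ratio 1.52:

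- Mean relative rate: (34 + 10 × 1.52)/44 = 1.118.
- Variance between groups: (34/44)(10/44)(0.52²) = 0.0475; divided by 1.118², 0.038.
- Variance within groups: 0.34² × 1.038 = 0.120.
- Total CV: √0.158 = 0.40, of which the new/PEOPLE split explains 0.038/0.158 = 24%.

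The same steps give a total CV of about 0.46 (40%) at ratio 1.82 and 0.55 (56%) at 2.27.

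**Simulation of the planned model.** Assumptions: clusters of 73,000/34 = 2,147 (PEOPLE) and 51,000/10 = 5,100 (new), times 0.73 × 0.83; gamma cluster effects; Poisson counts; one intercept per cluster; a Wald test, since 9.3.1 names none; 2022 prevalence and arms 1–4 unrelated to later incidence.

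| New/PEOPLE ratio | Model SE vs true SD of log IRR | Type I error |
|---|---|---|
| 1 (CV 0.4) | no excess | 5.4–5.8% |
| 1.52 | small excess | 3.4% (another run 5.2%) |
| 1.82 | 0.179 vs 0.158 | 3.1% |
| 2.27 | 0.196 vs 0.158 | 1.6% |

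The excess in SE is 13% at 1.82 (0.179/0.158) and 24% at 2.27 (0.196/0.158).

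**Power, planned model against a within-pair test.** At IRR 0.65: about 59% vs 63% (ratio 1.82) and about 52% vs 66% (ratio 2.27). At IRR 0.5 with total CV held at 0.4: 97% vs 98%.

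**Do the obvious repairs work?** Adding island, former arm and prevalence as covariates with an uncorrected Wald test gives type I error of about 8–10%. Re-randomization within pairs, adjusted only for new versus PEOPLE, gives 4.6–5.3%.

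**Fomboni.** With one intercept for both halves at 2,147 people each, type I error moves from 6.2% to 6.6% (ratio 1) or from 1.6% to 3.5% (ratio 2.27), which is the opposite direction. The effect of the distance covariate cannot be computed from the documents.

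**The case against.** The strongest case against is that the whole numerical effect rests on one inferred contrast, new against PEOPLE villages. For the former arms the documents point the other way: rate ratios of 1.23, 0.78 and 0.89, all with p ≥ 0.70. The 20–30 per 10,000 covers five years and may reflect different case finding. At a ratio near 1.5 the excess is small and simulations disagree on whether it is visible. At the planned CV of 0.4 and IRR 0.5 almost nothing is lost, and the error is conservative. Section 9 also leaves detail to a binding SAP, and a phase 3 SAP could still settle all of this.

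Most of that stands and limits the size of the point. It does not remove it. The protocol text is what exists for phase 3, it contradicts itself on distance, and it does not analyse the design as randomized.

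Three stronger readings are tempting and not supported:

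- **Differences among former arms 1–4 or in 2022 prevalence distort the result.** No figure in the documents shows that either predicts later incidence.
- **The trial is underpowered for its design effect.** Not at the planned parameters.
- **The shared Fomboni intercept seriously inflates type I error.** The large figures (6–15% in total) need 5,100 people in each half and independent halves. Fomboni's size is not given, halves of one town are probably alike, and section 4.2 uses village and cluster loosely, so the literal reading is itself doubtful.

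**Conclusion.** The point holds as a conditional loss of precision plus a contradiction in the text. The primary model does not reflect the pairs, names the wrong unit for one village of 43, and exists in two forms as regards distance. With a new/PEOPLE ratio of about 1.5 to 2.3, type I error falls to roughly 3.4% and then 1.6%, and power is lost for effects smaller than IRR 0.5. With no contrast there is no excess width.

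These figures depend on the inferred ratio, a within-group CV of 0.34, a Wald test and average cluster sizes, and the power figures are good to a few points. The textual parts need no assumption. The change is worth making because it is inexpensive and closes an open choice of primary model; it does not bear on the validity of a positive result.

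**What to change.** In section 9.3.1, and by reference in 9.3.2 and 9.3.3:

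- Make each of the 44 randomized clusters the random-effect unit, so that the two halves of Fomboni have separate intercepts.
- Adjust for island and for new versus former PEOPLE village. Former arm and 2022 prevalence then act through the pairing.
- Take the p-value from re-randomizing arm within the 22 pairs, and the 95% interval as the set of rate ratios that this test does not reject. Another small-sample-valid analysis that respects the pairs would also serve. Do not use an uncorrected Wald test with many cluster-level covariates.
- State one covariate list, with or without distance to the nearest index case, and make the synopsis, section 3.1 and 9.3.1 agree.

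The cost is a wording change, a short program using data already collected, and about 2 to 6 power points if the pairing proves uninformative. How arm 1 participants who received SDR-PEP are handled is a separate question and is not part of this change.
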